16.2.2 Sample Size

This study is expected to need to accrue 108 evaluable patients unless the study is closed early for excessive toxicity. We anticipate approximately 10% lost to follow-up due to 120 day endpoint, therefore we anticipate accruing an additional 12 patients to account for ineligibility, cancellation, or other reasons, making the overall sample size of 120 patients.

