16.1.1 Primary Endpoint

The primary endpoint of this trial is the proportion of patients who experience major wound complications within 120 days of surgical resection of soft tissue sarcoma of the extremity and superficial trunk following preoperative radiation therapy of 42.75 Gy in 15 fractions. Major wound complication is defined as secondary unplanned operation under general or regional anesthesia for wound repair (e.g., debridement, operative drainage, or secondary wound closure including rotationplasty, free flaps or skin grafts); or wound management without secondary operation including invasive procedures (e.g., aspiration of seroma or readmission for wound care such as intravenous antibiotics or persistent deep packing for 120 days or longer). All patients meeting the eligibility criteria who have signed a consent form and have begun treatment will be evaluable for the primary endpoint.

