16.2 Statistical Design

The non-inferiority one-sample test was utilized from PASS software for this design (Non-Inferiority of One Proportion using the Z-Test with S(P0) in PASS 16.0.4). A sample size of 108 evaluable patients achieves 80% power (1-sided significance level of 10%) to detect a non-inferiority margin of 10%, assuming that any major wound complication rate of 45% or above is inferior as compared to the current standard of care complication rate of 35%.⁶ We hypothesize that the proposed hypofractionated preoperative radiation therapy of 42.75 Gy in 15 fractions is not inferior to the conventional fractionation of 50 Gy in 25 fractions

by showing the complication rate is $< 45\%$ for the proposed treatment (non-inferiority margin of 10%).

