16.2.1 Decision Rule

After the first 108 eligible patients have completed 120 days post-treatment, we'll do the final analysis of the data, and if the Z-test is significant at the 10% significance level, we'll conclude that hypofractionated preoperative radiation therapy of 42.75 Gy in 15 fractions is not inferior to conventional fractionation of 50 Gy in 25 fractions and can be tested further in larger studies.

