16.2.4 Power and Significance Level

Assuming that the number of major wound complications is binomially distributed, the significance level is 0.1 i.e. there is 10% chance of finding hypofractionated preoperative radiation therapy to be effective when it truly is not. The probability of declaring that the proposed radiation therapy warrants further studies (i.e., statistical power) is 80.01%, if the true acute wound complication is $<45\%$.

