16.3.1 Primary Outcome Analysis

16.3.1.1 Definition: The primary endpoint of this trial is the proportion of patients who experience major wound complications within 120 days of surgical resection of soft tissue sarcoma following preoperative radiation therapy. All patients meeting the eligibility criteria who have signed a consent form and have begun treatment will be evaluable for the major wound complication rate.

16.3.1.2 Estimation: The proportion of major wound complications will be estimated by the number of patients who experience the major wound complications within 120 days following surgery divided by the total number of evaluable patients. 95% confidence intervals using normal approximation to binomial wound complication proportion will be calculated.

16.3.1.3 Over Accrual: If more than the target number of patients are accrued, the additional patients will not be used to evaluate the stopping rule or used in any decision making process; however, they will be included in final endpoint estimates and confidence intervals.

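### The plan defines the day-120 evaluable set in conflicting ways, and under its written formula unseen complications can only push the 45% test toward non-inferiority

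*Combined protocol and SAP*

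**What the plan says.** Four parts of the statistical section bear on who is counted.

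- **Sizing.** Section 16.2 states that "A sample size of 108 evaluable patients achieves 80% power". Section 16.2.2 then says "We anticipate approximately 10% lost to follow-up due to 120 day endpoint, therefore we anticipate accruing an additional 12 patients" and arrives at 120. The same sentence also assigns the 12 extra patients to ineligibility, cancellation and other reasons.
- **Evaluable set.** Section 16.1.1 says that patients who are eligible, have consented and "have begun treatment will be evaluable for the primary endpoint". Section 16.3.1.1 repeats this. Neither requires known wound status at day 120.
- **Estimator.** Section 16.3.1.2 defines the rate as "the number of patients who experience the major wound complications within 120 days following surgery divided by the total number of evaluable patients".
- **Decision set.** Section 16.2.1 runs the final test "After the first 108 eligible patients have completed 120 days post-treatment". Section 16.3 ties the start of analysis to the time when patients have become evaluable, which suggests that evaluability is reached over time and not when treatment starts.

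The only rule that makes a patient inevaluable and replaceable, Section 13.3, covers failure to complete radiation for reasons other than toxicity. Section 4.0, footnote 9, ends study assessments for patients who progress or will not return. No section gives a missing-outcome or censoring rule for the primary endpoint.

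**The concern.** The sample size assumes that a patient lost before day 120 leaves the analysis and is made up from the reserve. The evaluable definition and the estimator keep that patient in. Applied as written, a resected patient last seen on day 60 without a complication adds one to the denominator and nothing to the numerator, so days 61 to 120 are treated as observed and event-free.

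The direction of the error is fixed. A missed complication lowers the observed rate and cannot raise it. The trial has one arm and tests against a constant 45%, so no control group shares the error. The reserve meant to absorb losses would then protect neither the type I error nor the estimate. With several readings available, the choice could also be made after the outcomes are known.

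**Working it through.** **Inputs from the plan (Sections 16.2 and 16.2.2).** Limit 45%, assumed true rate 35%, one-sided 10% level, 108 evaluable, about 10% loss, 120 accrued. The test is "Non-Inferiority of One Proportion using the Z-Test with S(P0) in PASS 16.0.4", so the variance is taken at 45%.

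**Assumptions not in the documents.** L is the proportion lost among the 108 tested, shown at 5% and 10%. q is the share of lost patients' complications recorded before loss, shown from 100% to 0%. Lost patients are given the same true rate as the others.

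**1. Reproduce the plan.**
n = [(1.2816 × √(0.45 × 0.55) + 0.8416 × √(0.35 × 0.65)) / 0.10]² = 107.95, so 108. Normal-approximation power at 108 is 80.01%, as Section 16.2.4 states. 108 / 0.9 = 120. The sizing is correct, and it matches losses that leave the 108.

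**2. Pass mark.**
z = (x/108 − 0.45) / √(0.45 × 0.55 / 108) must be at or below −1.2816. x = 41 gives −1.470 and x = 42 gives −1.277, so the test passes at 41 or fewer (38.0%). Exact binomial type I error is P(X ≤ 41 | 108, 0.45) = 8.4%. Exact power at 35% is 77.4%.

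**3. Losses scored by the written formula.**
Apparent rate = 0.45 × (1 − L + Lq). Exact type I error is P(X ≤ 41 | 108, apparent rate).

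| Captured before loss (q) | 5% loss: apparent rate | Type I error | 10% loss: apparent rate | Type I error |
|---|---|---|---|---|
| 100% | 45.0% | 8.4% | 45.0% | 8.4% |
| 75% | 44.4% | 10.4% | 43.9% | 12.7% |
| 50% | 43.9% | 12.7% | 42.8% | 18.2% |
| 25% | 43.3% | 15.3% | 41.6% | 25.1% |
| 0% | 42.8% | 18.2% | 40.5% | 33.2% |

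Put another way, if exactly 11 of 108 are lost with nothing captured, the test passes at up to 41/97 = 42.3% among followed patients, against the intended 41/108 = 38.0%.

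**4. Check of an obvious repair.**
Suppose lost patients count only if they had a complication, and event-free losses are dropped and replaced. With 10% loss and 108 counted, the expected rate at a true 35% is 0.35 × (0.9 + 0.1q) / (0.9 + 0.1q × 0.35). Exact power falls from 77.4% to 73.0%, 68.4%, 63.6% and 58.7% at q = 25%, 50%, 75% and 100%. At q = 100%, type I error drops to 2.7%. This rule is biased the other way.

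**5. Worst-case scoring.**
If 11 of 108 are lost and all count as complications, a pass needs 41 − 11 = 30 or fewer among the other 97. Exact power at 35% is then about 23%. This is useful as a bound but too severe as a pass/fail criterion.

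**The case against.** The strongest reply is that the plan never says lost patients are complication-free. A reader might infer such a rule, but it follows only from the Section 16.3.1.2 formula combined with silence on missing outcomes. Sections 16.2.1 and 16.3 permit a reading in which only patients followed to day 120 enter the test and the reserve replaces the rest. On that reading the bias in step 3 does not reach the test. This stands as a possibility but does not settle the matter. Section 16.2.1 says eligible where it would need to say followed, works equally well as a timing trigger, and counts from treatment while the endpoint counts from surgery.

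The loss rate is also open to challenge. The 12 extra patients cover ineligibility and cancellation too, so 10% is an upper value for loss among tested patients. That is correct, and it is why 5% is shown.

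Capture may be good. Section 4.0 schedules wound assessment at 4-8 weeks and again at the six-monthly visits, and allows remote contact. Appendix VI records the complication start date separately from the notification date, so late reports can be dated back. Against this, footnote 9 ends assessments for some patients, and the documents give no figures on when complications occur.

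A death before day 120 without a complication should not be grouped with losses. It is an observed non-event, and a competing-risk estimate treats it so.

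**Conclusion.** The conflict stands. The sizing excludes losses, the evaluable definition and estimator include them, and the decision rule can be read either way. Under the written estimator the direction of bias is certain and its size is not. For the 108-patient test, exact type I error at a true 45% moves from 8.4% to 10-18% with 5% loss and 13-33% with 10% loss, over 75% to 0% capture.

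A reader might infer that the trial carries a one-in-three chance of a false non-inferiority claim. The documents do not support that. The 33% figure needs the full 10% loss among tested patients, no complication recorded before any loss, and the literal formula applied to the test. With full capture the formula has no bias. The supportable conclusion is that the primary analysis set is unresolved and one of its written readings is anti-conservative. This should be corrected before the primary data are examined.

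**What to change.** 1. Reconcile Sections 16.1.1, 16.2.1, 16.2.2 and 16.3.1 to one analysis set, counted from surgery and chosen by enrolment order, not by completeness of follow-up. State whether it is the first 108 or up to 120, and how eligible patients who are never resected are reported.
2. State that unknown day-120 wound status is not counted as complication-free.
3. Base the primary estimate and the one-sided 10% test against 45% on the day-120 cumulative incidence of major wound complication from surgery. Censor at last wound contact and treat death without a complication as a competing event. With no losses this estimate equals the simple proportion. Specify the variance: at 42/108 the estimated variance gives z = (0.3889 − 0.45) / √(0.3889 × 0.6111 / 108) = −1.30, a pass, whereas the plan's null variance gives −1.277, a fail.
4. Add a sensitivity test that counts lost patients as complications. It should inform interpretation and not act as a second hurdle (step 5).
5. Do not adopt a rule that keeps lost patients' complications but drops event-free losses (step 4).

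**Cost.** Revised wording, a recorded date of last wound contact, slightly more analysis work, and a slightly wider interval when patients are censored. No extra patients are needed. The estimate assumes that censored patients have the same later risk as those still followed, and the sensitivity test probes that assumption.

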16.2.3 Accrual Rate and Study Duration

The expected accrual rate is about 4 patients per month. With this accrual rate, we expect to finish accrual within about 30 months of study activation, assuming we accrue 120 total patients. The final analysis can begin as soon as the last patient has been observed for 4 months post treatment, or at approximately 3 years after the study opens to accrual.

16.2.4 Power and Significance Level

Assuming that the number of major wound complications is binomially distributed, the significance level is 0.1 i.e. there is 10% chance of finding hypofractionated preoperative radiation therapy to be effective when it truly is not. The probability of declaring that the proposed radiation therapy warrants further studies (i.e., statistical power) is 80.01%, if the true acute wound complication is $<45\%$.

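### Section 16.2.4 gives 80.01% power for any true complication rate below 45%, but that is the power at 35%; the same formula gives 40% at a true 40% and 14% at 44%.

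*Combined protocol and SAP*

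**What the plan says.** Section 16.2 sets up a one-sample non-inferiority test, "Non-Inferiority of One Proportion using the Z-Test with S(P0) in PASS 16.0.4". It takes 35% as the standard-of-care major wound complication rate and treats 45% or above as inferior. It then states: "A sample size of 108 evaluable patients achieves 80% power (1-sided significance level of 10%) to detect a non-inferiority margin of 10" percentage points. It does not say in words that power is evaluated at a true rate of 35%.

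Section 16.2.1 declares non-inferiority in the first 108 eligible patients "if the Z-test is significant at the 10% significance level". It gives no event count.

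Section 16.2.4 describes the operating characteristics. It begins "Assuming that the number of major wound complications is binomially distributed, the significance level is 0.1" and then gives the power: "The probability of declaring that the proposed radiation therapy warrants further studies (i.e., statistical power) is 80.01%, if the true acute wound complication is" below 45%. No section gives power at any other true rate.

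**The concern.** A true rate below 45% is the claim the trial sets out to establish. It is a range, and power varies across it. As the true rate approaches 45%, power must fall to the significance level, which section 16.2.4 itself puts at 10%. A single figure of 80.01% therefore cannot hold over the range.

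What is at stake is how the result is read. Someone relying on section 16.2.4 would think that a regimen whose true rate is 40%, acceptable under the plan's own margin, would pass four times in five. A failed test would then look like strong evidence that the rate is 45% or more, when the trial had little chance of passing a regimen in the upper half of the margin.

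A smaller gap adds to this. The section assumes a binomial count, but the plan never converts the Z-test into the number of complications that decides the trial.

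**Working it through.** **Inputs** (section 16.2, with alpha repeated in 16.2.4): n = 108; null rate P0 = 0.45; reference rate 0.35; one-sided alpha 0.10, so z = 1.2816; standard error computed under the null, S(P0).

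**1. The plan's sample size reproduces.**

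n = [(1.2816·√(0.45·0.55) + 0.8416·√(0.35·0.65)) / 0.10]² = [(1.2816·0.4975 + 0.8416·0.4770) / 0.10]² = 107.95, rounded up to 108.

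**2. The plan's power reproduces at a true rate of 35%.**

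The test passes when the observed proportion is below c = 0.45 − 1.2816·√(0.45·0.55/108) = 0.45 − 1.2816·0.04787 = 0.38865.

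Power(p) = Φ[(c − p) / √(p(1−p)/108)].

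At p = 0.35: (0.38865 − 0.35)/0.04590 = 0.842, and Φ(0.842) = 0.8001. Solving the formula for 80.01% returns p = 0.350. Using the estimated-variance form instead gives 81.5% at 35%, and adding a continuity correction to the S(P0) form gives 77.1%. So 80.01% belongs to the named test at 35%.

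**3. The same formula at other rates below 45%.**

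- p = 0.40: (0.38865 − 0.40)/0.04714 = −0.241, power 0.405.
- p = 0.44: (0.38865 − 0.44)/0.04776 = −1.075, power 0.141.

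**4. The event cutoff.** c·n = 41.97, so 41 events pass and 42 fail:

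- 41/108: z = (0.3796 − 0.45)/0.04787 = −1.470, one-sided p = 0.071.
- 42/108: z = (0.3889 − 0.45)/0.04787 = −1.277, one-sided p = 0.101.

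The call at 42 is very close and depends on the variance form. With the estimated variance, z = (0.3889 − 0.45)/√(0.3889·0.6111/108) = −0.0611/0.0469 = −1.303, p = 0.096, and 42 would pass.

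**5. Exact binomial probability of 41 or fewer events in 108,** beside the normal approximation:

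| True rate | Normal approximation | Exact |
|---|---|---|
| 30% | 97.8% | 97.0% |
| 35% | 80.0% | 77.4% |
| 38% | 57.3% | 53.9% |
| 40% | 40.5% | 37.2% |
| 42% | 25.5% | 22.7% |
| 44% | 14.1% | 12.1% |
| 45% (alpha) | 10.0% | 8.4% |

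Exact power reaches 80% only at true rates of 34.6% or lower and is 50% at 38.5%. Allowing 42 events would raise exact alpha to 11.9%. The 2.6-point gap at 35% (80.0% against 77.4%) comes from the count being discrete; it is not a sample-size error.

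**The case against.** The best defence is that nothing has been miscalculated. The sample size and the 80.01% both reproduce, and a statistician can recover the 35% alternative from section 16.2. That is true, and it is why this is a wrong condition on a correct number and not a flaw in the design. But section 16.2 presents 35% as the standard-of-care rate, and section 16.2.4 is the only place that states when the power applies.

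It is also fair that the range below 45% includes rates below 35%, where power exceeds 80% (97.8% at 30%), so the figure is a valid minimum there. It is not a minimum between 35% and 45%, which is the whole of the margin.

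On the cutoff, the objection is that 41 follows from the named test with 108 patients, so the rule is not undefined. That stands, provided the S(P0) form is carried from the design in 16.2 into the analysis in 16.2.1, which mentions only a Z-test. It is also true that the exact figures hold only if exactly 108 patients enter the decision: the same Z-test rule has exact alpha 9.8% and power 79.5% with 107 patients, and 8.9% and 78.9% with 110. Sections 16.2.1 and 16.3.1.3 do fix the decision on the first 108, but the text should state that dependence.

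**Conclusion.** The power statement in section 16.2.4 is wrong as written. The 80.01% applies at a true rate of 35%. Between 35% and 45% it overstates power by an amount that grows to about 70 points as the true rate nears 45% (80% against 10%). At a true 40% the chance of passing is 40.5% by the plan's own approximation and 37.2% exactly; at 44% it is 14.1% and 12.1%.

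The sample size, test and decision rule are not in question, and the primary analysis does not use the power sentence. The harm is to anyone judging the trial's sensitivity or interpreting a negative result. These figures rest on the S(P0) Z-test without continuity correction, one-sided alpha of 10%, and exactly 108 patients in the decision.

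**What to change.** In section 16.2.4, replace the condition of a rate below 45% with a true rate of 35%. Name 35% as the power alternative in section 16.2, and put the cutoff in section 16.2.1. Text that would serve:

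*Power is 80.01% by normal approximation if the true complication rate is 35%. With 108 patients in the decision, non-inferiority is declared at 41 or fewer complications. The exact one-sided alpha of this rule is 8.4%; its exact power is 77.4% at a true rate of 35%, 37.2% at 40% and 12.1% at 44%. If the number of patients in the decision is not 108, the cutoff and these figures are recalculated from the same S(P0) Z-test.*

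The essential part is the change from below 45% to 35%; the cutoff and exact figures settle in advance the close call between 41 and 42 events.

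An optional reporting aid, separate from the correction: at 39 to 41 events the trial is positive while the upper limit of the planned 95% normal-approximation interval (section 16.3.1.2) is 45.2% to 47.1%. A two-sided 80% Wilson interval reported beside it would agree with the test (upper limit 44.1% at 41 events, 45.02% at 42).

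The cost is wording in three subsections. Nothing changes for patients, sample size, test or decision rule. The plan would show an exact power slightly under the nominal 80%.

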16.2.5 Other Considerations

Adverse events, quality/duration of response, and patterns of treatment failure observed in this study, as well as scientific discoveries or changes in standard care will be taken into account in any decision to terminate the study.

16.3 Analysis Plan

The analysis for this trial will commence at planned time points (see 16.2.3) and at the time the patients have become evaluable for the primary endpoint. The Statistician and Study Chair will make the decision, in accord with CCS Standard Operating Procedures, availability of data for secondary endpoints (e.g., disease free survival, overall survival), and the level of data maturity. It is anticipated that the earliest date in which the results will be made available via manuscript, abstract, or presentation format is when last patient has been followed for at least 6 months.

Note: Both primary and secondary outcomes will be compared between anatomical sites (proximal lower limb (includes knee) vs rest). The comparison between groups will be exploratory in nature.

16.3.1 Primary Outcome Analysis

16.3.1.1 Definition: The primary endpoint of this trial is the proportion of patients who experience major wound complications within 120 days of surgical resection of soft tissue sarcoma following preoperative radiation therapy. All patients meeting the eligibility criteria who have signed a consent form and have begun treatment will be evaluable for the major wound complication rate.

16.3.1.2 Estimation: The proportion of major wound complications will be estimated by the number of patients who experience the major wound complications within 120 days following surgery divided by the total number of evaluable patients. 95% confidence intervals using normal approximation to binomial wound complication proportion will be calculated.

16.3.1.3 Over Accrual: If more than the target number of patients are accrued, the additional patients will not be used to evaluate the stopping rule or used in any decision making process; however, they will be included in final endpoint estimates and confidence intervals.

16.3.2 Secondary Outcome Analysis

16.3.2.1 Local failure is defined any radiographic or pathologic evidence of recurrent disease inside the CTV and/ or to within 3 cm from the edge of the CTV. In the absence of censored patients prior to 5 years, local failure rate at 5 years (LFR5) will be equal to the binomial proportion. LFR5 will be evaluated by the number of patients free of local failure/recurrence at 5 year divided by the total number of evaluable patients. Exact binomial 95%

confidence interval for the point estimate will be provided. In the case of censoring prior to 5 years, LFR5 will be estimated using the Kaplan-Meier method.

- 16.3.2.2 Disease-Free Survival is defined as the time from registration date to the earliest date of documentation of either, local recurrence, regional recurrence, distant recurrence, or death due to any cause, censoring patients who are alive and local recurrence free at the date of last known clinical assessment. The distribution of disease-free survival will be estimated using method of Kaplan-Meier.
- 16.3.2.3 Overall Survival is defined as the time from registration date to death due to any cause, censoring patients alive at the date of last contact. The distribution of overall survival will be estimated using method of Kaplan-Meier.
- 16.3.2.4 Late toxicity is defined as toxicity occurs any time between 3 months and 24 months after completion of hypofractionated preoperative radiation therapy. The rate of \geq grade 2 late toxicities will be estimated by the number of patients with a \geq grade 2 late toxicity divided by the total number of evaluable patients. Exact binomial 95% confidence intervals for the true rate of \geq grade 2 toxicity events will be calculated.
- 16.3.2.5 Pattern of relapse will be evaluated by number of patients with patterns of tumor recurrence such as local recurrence, marginal recurrence, regional recurrence, distant metastasis, and second primary tumor divided by the total number of evaluable patients. Exact binomial 95% confidence interval for the point estimate will be provided.
 - 16.3.2.5.1 Local tumor recurrence is defined as any tumor recurrence inside the CTV.
 - 16.3.2.5.2 Marginal tumor recurrence is defined as any tumor recurrence beyond the CTV to within a 3 cm distance from the edge of the CTV.
 - 16.3.2.5.3 Distant tumor recurrence is defined as any tumor that develops distantly from the primary site of sarcoma.

- 16.3.2.5.4 Second primary tumor is defined as any different histology of sarcoma or any other type of malignancy inside or outside the radiation field.
- 16.3.2.6 Adverse Events: All eligible patients that have initiated treatment will be considered evaluable for assessing adverse event rate(s). The maximum grade for each type of adverse event will be recorded for each patient, and frequency tables will be reviewed to determine patterns. Additionally, the relationship of the adverse event(s) to the study treatment will be taken into consideration. Late toxicities (as defined in sections 16.3.2.4) will be summarized separately.
- 16.3.2.7 Quality of Life Measurements – PROMIS-10: Results from the ten-item PROMIS questionnaire will be used to evaluate physical health and mental health, separately. Changes in raw score from baseline to 24-months post-surgery will be assessed, in each of the physical and mental health domains. The Wilcoxon signed-rank test will be utilized to assess changes in raw PROMIS scores. Mean change, along with standard deviation will be reported.
- A scoring table to compare this patient population to global means may be utilized for various timepoints. However, because this scoring table is prepared for a fixed set of items, it can only be used when an examinee responds to all of the items in the set. This, along with all other analyses, including graphical representations and comparisons between other timepoints or subgroups of patients may be performed, but will be considered exploratory.
- 16.3.2.8 Quality of Life Measurements – TESS: Results from the Toronto Extremity Salvage Score (TESS) questionnaire will be used to evaluate functional outcomes. The TESS specifically measures performance of activities of daily living, and is separated into upper and lower extremity versions (29 and 30 questions, respectively).
- Patients will fill out the appropriate version, and point totals will be summed. Mean change from baseline to 24 months post-surgery, along with standard deviation will be reported by version. The Wilcoxon signed-rank test will be used to assess changes in TESS scores within questionnaires. All other analyses, including graphical representations, GEE model creation, and comparisons between different timepoints or subgroups of patients may be performed, but will be considered exploratory.

